6. PATIENT POPULATION

6.1. Patient Selection

This study can fulfill its objectives only if appropriate patients are enrolled. The following eligibility criteria are designed to select patients for whom cryoablation therapy is considered appropriate. All relevant medical and non-medical conditions should be taken into consideration when deciding whether cryoablation therapy is suitable for a particular patient.

6.2. Inclusion Criteria

Eligible patients for this study must meet all of the following criteria:

- 6.2.1. Patient must be at least 18 years old.
- 6.2.2. Patient has signed a written informed consent.
- 6.2.3. Patient presents with Stage 4 pulmonary metastatic disease with metastatic disease previously confirmed by prior biopsy;
or
Patient presents with Stage 4 pulmonary metastatic disease previously confirmed on imaging (e.g. CT) with histology proven primary cancer.
- 6.2.4. Patient has up to 6 local pulmonary metastases targetable by cryoablation.
- 6.2.5. Targeted index tumor(s) defined as intra pulmonary or pleural with a maximum size of 3.5 cm, measured in the longest cross sectional dimension.
- 6.2.6. The target index tumor(s) is determined (by CT images) to be in a location where cryoablation is technically achievable based on the proximity of adjacent organs/ structures and is greater than 0.5 cm from any critical organ/structure (possibly achieved with additional maneuvers such as iatrogenic pneumothorax or hydrodissection).
- 6.2.7. Karnofsky Performance Scale (KPS) score ≥ 60 .
- 6.2.8. Platelet count $>50,000/\text{mm}^3$ within 8 weeks prior to initial cryoablation procedure.
- 6.2.9. INR <1.5 within 8 weeks prior to initial cryoablation procedure.
- 6.2.10. Patient has a life expectancy of >3 months.

6.3. Exclusion Criteria

Patients not eligible for participation in this study include patients who have any of the following:

- 6.3.1. Patient's index tumor(s) is primary lung cancer.
- 6.3.2. Patient has uncontrollable primary or metastatic disease outside of the lung.
- 6.3.3. Patient is unable to lie flat or has respiratory distress at rest.
- 6.3.4. Patient has a coagulopathy or bleeding disorder which is uncontrolled.
- 6.3.5. ANC <1000 within 8 weeks prior to initial cryoablation procedure.
- 6.3.6. Patient has evidence of active systemic, pulmonary, or pericardial infection.
- 6.3.7. Patient has a debilitating medical or psychiatric illness that would preclude giving informed consent or receiving optimal treatment or follow up.
- 6.3.8. Patient is currently participating in other experimental studies that could affect the primary endpoint (e.g. experimental chemotherapy regimen).

THE REMAINDER OF THIS PAGE IS INTENTIONALLY LEFT BLANK

7. STUDY PROCEDURES

The study schedule of events and the specific procedures performed at each visit are shown in Table 1, Schedule of Events. Each patient will undergo a total of 9 visits, including an initial/screening visit, the procedure visit, and 7 post-operative visits. More visits may be required when medically necessary.

Table 1: Schedule of Study Events

Procedures	Screening ^a	Procedure Date	W 1 ^c	M 1 ^e	M 3 ^{g,h,i}	M 6, 12, 18, 24 or W/D ^{g,h,i}
Informed Consent	X					
Inclusion/Exclusion	X					
Demographics	X					
Targeted Medical History	X					
Karnofsky Performance	X			X	X	X
Pertinent Medication	X		X	X		
Discontinue anticoagulation, as clinically indicated	X	X				
Imaging Scan	X ^f		X ^d	X ^f	X ^f	X ^f
Record index tumor characteristics	X					
Cryoablation procedure		X ^b				
Labs	X					
Quality of Life (SF-12)	X			X	X	
Safety Assessment		X	X	X	X	X

^a All screening visit requirements should be within 8 weeks of the initial cryoablation procedure. Any items (e.g., imaging or lab assessment) previously conducted as routine standard of care prior to the signed informed consent may be used to satisfy the screening requirements provided they are completed within 8 weeks of the initial cryoablation procedure.

^b If multiple tumors are planned for study inclusion, treatment of all study index tumors should be completed within an 8 week window.

^c The week 1 follow up visit may take place prior to discharge from the hospital or within 1 week (7 days) of the cryoablation procedure.

^d Week 1 imaging may be a chest CT ± contrast or chest X-Ray

^e Month 1 visit window 30 days -7/+21 days

^f Chest CT scan ± contrast (contrast is preferred)

^g Months 3, 6, 12, 18 and 24 visit window +/- 30 days

^h In the event of multiple cryoablation procedure dates, the most recent procedure date will serve as the reference for determining the follow up visit window.

ⁱ While return visits are preferred to be conducted in the clinic setting, in the event the patient is not able to return due to distance or illness, follow up assessments (i.e. all assessments with the exception of imaging) may be conducted via telephone or tele-video (e.g. Skype). Tele-video should only be considered if the patient has the knowledge and access to such technology.

7.1. Patient Enrollment

To minimize selection bias within the enrolled patient population, participation in the study is to be offered to all eligible patients on a consecutive basis as they present to the physician at the site. All eligible patients will be assigned a screening number. The screening log will include minimal health information regarding each non-enrolling patient (e.g., sex, age, reason for not enrolling, etc.). As the non-enrolled patients will not sign an informed consent form the data collected will not include personally identifiable information (as defined in 45 CFR 164.514).

Patients who wish to participate in this study and sign a written informed consent form will be assigned a unique identifier number at baseline to be used throughout the study.

7.2. Screening

The screening visit allows the investigator to assess a patient's eligibility for this study.

The following assessments will be used to support patient enrollment and shall be performed within 8 weeks of the initial cryoablation procedure. Any items (e.g., imaging or lab assessment) previously conducted as routine standard of care prior to the signed informed consent may be used to satisfy the screening requirements provided they are within 8 weeks of the initial cryoablation procedure.

- Informed consent;
- Review inclusion/exclusion criteria;
- Patient number assigned;
- Demography;
- Targeted medical history, including comorbidities;
- Karnofsky Performance Scale;
- Baseline labs (Platelet Count, ANC and INR);
- CT scan of chest ± contrast (contrast is preferred);
- Baseline index tumor characteristics (See Section 5.4);
- Quality of Life assessment (SF-12);
- Current pertinent concomitant medication;
- Discontinue anticoagulation as clinically indicated;

7.3. Cryoablation

7.3.1. Treatment of Multiple Metastatic Lung Tumors

Treatment of all study index tumors should be completed within an 8 week window. Tumors contained in both lungs should be treated in an appropriate interval determined on an individual basis. It is not recommended that bilateral index tumors be treated in a single treatment session.

7.3.2. Cryoablation Procedure

For cryoablation, patient preparation, anesthesia, intra-operative monitoring, and post-operative management are identical to those of standard cryoablation treatments routinely performed at all clinical centers participating in this study and are at the discretion of the investigator.

Galil Medical's Cryoablation System will be used per the manufacturer's guidelines. Galil Medical's cryoablation needles will be placed under CT image guidance in a pattern necessary to fully freeze the target tumor(s). The treatment will be administered utilizing cryoablation needles with

compressed argon gas through the Joule-Thomson effect to produce extremely low temperatures within the target tumor(s).

The following data will be collected at the time of the procedure or prior to discharge, as applicable:

- ASA Physician Status Classification (Appendix E)
- Number of tumors treated with cryoablation;
- Index tumor size measurement:
 - 3 axes of measurements (cm) (largest diameter and two perpendicular diameters)
- Number and type of cryoablation needles used;
- Number of freeze and thaw cycles;
- Freeze and thaw times, per cycle;
- Number and type of intra-operative complication(s)
 - Severity of complication(s);
- Length of hospital stay;
- Total procedure time;
- Anesthesia type;
- Additional surgical intervention(s);
- Safety assessment.

7.3.3. Cryoablation needle placement

The number and configuration of the needles will be based on the necessity to maintain appropriate distances between adjacent cryoablation needles and anatomic structures, and the final number of needles can only be formulated based upon the configuration of the index tumor(s) at the time of treatment. The use of a single needle per tumor should be avoided as it is well understood there is a benefit to multiple needles as a result of ice coalescence and the potential for increased risk of recurrence. The CT imaging views of the index tumor(s) will enable final assessment of the percutaneous access route and needle placement on the day of the procedure. Cryoablation needles will be placed to create multiple overlapping iceballs to completely cover the index tumor and provide a 5 mm zone of ablation surrounding the index tumor while maintaining appropriate safe distance from the non-targeted tissues (i.e. main bronchus and pulmonary arteries).

7.3.4. Cryoablation needle testing

Before anesthesia inducement of the patient, all cryoablation needles should be tested in accordance with Galil Medical's Cryoablation System User Manual to confirm their freezing function and structural integrity.

7.3.5. Freezing procedure

Once freezing has been initiated, the cryoablation procedure will be monitored with CT ± contrast imaging to visualize iceball growth, to ensure the ablation zone is adequately frozen and adjacent anatomical structures are protected. As the freezing continues, the ice formation from each of the cryoablation needles coalesce so the targeted portions of the ablation zone are frozen.

The guideline for pulmonary cryoablation is typically 3 freeze/thaw cycles. The following three cycle freeze-thaw protocol is suggested to be employed:

- Cycle 1: Freeze 3 minutes followed by passive thaw for 3 minutes;
- Cycle 2: Freeze 7-12 minutes followed by passive thaw for 3 minutes;
- Cycle 3: Freeze 7-12 minutes followed by active thaw in order to aid in the removal of the cryoablation needles.

7.3.6. Procedure completion

CT images are typically obtained in the transverse and longitudinal planes showing the greatest extent of freeze. The ice should encompass the entire tumor extending beyond the tumor margin in all dimensions with a goal of >5mm. After cryoablation needle removal, CT images will be obtained to assess any bleeding or pneumothorax development. If any adverse event is diagnosed it should be managed per standard of care.

An antibiotic of choice can be prescribed if needed according to center preferences in order to prevent post-operative infection.

7.4. Week 1 – Follow-up

The week 1 follow up visit may take place prior to discharge from the hospital or within 1 week (7 days) of the cryoablation procedure. Patients are to complete the following assessment:

- Chest X-Ray or chest CT scan \pm contrast (contrast is preferred) to identify possible post-procedure adverse events (may be assessed by last CT scan of the cryoablation procedure);
- Safety assessment;
- Current pertinent concomitant medication.

7.5. Month 1 – Follow-up

Patients will return 1 month (30 days $-7/+21$) post cryoablation procedure. In the event of multiple cryoablation procedure dates, the most recent procedure date will serve as the reference for determining the follow up visit window.

The following assessments will be completed:

- Quality of Life assessment (SF-12);
- Karnofsky Performance Scale;
- Safety assessment;
- Chest CT scan \pm contrast (contrast is preferred) to identify possible post-procedure adverse events. This 1 month imaging will serve as the new baseline for tumor response evaluation;
- Assessment of metastatic lung disease progression beyond the index tumor(s) and feasibility of treatment;
- Assessment of local tumor recurrence at the index tumor, including additional treatment and feasibility of treatment;
- Assessment of any systemic cancer treatment(s);
- Assessment of any local therapy for the index tumor(s).
- Current pertinent concomitant medication.

7.6. Month 3 – Follow-up

Patients will return at 3 months (+/-30 days) post cryoablation procedure. In the event of multiple cryoablation procedure dates, the most recent procedure date will serve as the reference for determining the follow up visit window.

The following assessments will be completed:

- Quality of Life assessment (SF-12);
- Karnofsky Performance Scale;
- Chest CT scan \pm contrast (contrast is preferred);
- Safety assessment;
- Assessment of metastatic lung disease progression beyond the index tumor(s) and feasibility of treatment;
- Assessment of local tumor recurrence at the index tumor, including additional treatment and feasibility of treatment;
- Assessment of any systemic cancer treatment(s);
- Assessment of any local therapy for the index tumor(s).

7.7. Months 6, 12, 18 and 24 – Follow-up

Patients will return 6, 12, 18, and 24 months (+/-30 days) post cryoablation procedure. In the event of multiple cryoablation procedure dates, the most recent procedure date will serve as the reference for determining the follow up visit window.

The following assessments will be completed:

- Karnofsky Performance Scale;
- Chest CT scan \pm contrast (contrast is preferred);
- Safety assessment;
- Assessment of metastatic lung disease progression beyond the index tumor and feasibility of treatment;
- Assessment of local tumor recurrence at the index tumor, including additional treatment and feasibility of treatment;
- Assessment of any systemic cancer treatment(s);
- Assessment of any local therapy for the index tumor(s).

7.8. Repeat Cryoablation Treatment(s) or Alternative Additional Treatment

Patients may receive additional cryoablation treatment(s) to the index tumor(s) initially subjected to cryoablation while participating in the study protocol. This additional cryoablation may be performed on the index tumor(s) provided that the additional treatment is performed with Galil Medical technology. In this situation, for each index lesion retreated, follow-up visits will restart per the study protocol and continue through the 24 month visit after the date of the repeat cryoablation treatment. When possible, if multiple tumors are present, all efforts should be made to align all follow up visits. For any index lesion not subjected to retreatment, the data collection continues per protocol.

- Baseline labs are recommended to be repeated prior to any repeat cryoablation procedure;
- It is recommended to discontinue anticoagulation as clinically indicated;

- SF-12 will not be collected prior to or after any repeat cryoablation of index tumor(s);
- Pertinent medications should be reviewed prior to and after any repeat cryoablation of index tumor(s);
- All other follow-up requirements are still applicable.

If other local treatment (e.g. radiofrequency ablation, microwave ablation, surgery, radiation) is used on the index tumor(s) initially treated, then the patient must be withdrawn from the study.

Data will be collected regarding any systemic cancer therapy the patients receive during the course of the study.

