10.5.5. Other Data Assessments

Technically successful treatment definition

A technically successful treatment will be defined by the presence of an ablation zone, ground glass opacity, or frank consolidation encompassing the targeted index tumor(s) no later than the 1 month follow up visit after the cryoablation procedure. Technical success will be analyzed on a per tumor basis.

Disease recurrence or progression definitions

The reference date for disease progression evaluation will be associated with the initial (first) cryoablation procedure done per study protocol. In the event of multiple cryoablation procedure dates, such as with bilateral lesions or staged treatments, the date of reference for disease progression evaluation will be the initial (first of n) cryoablation procedure.

- **Local disease progression** will be determined locally by evidence of local tumor failure.
- **Lung-disease-specific survival rate** is defined as the time in days from the first cryoablation procedure to death and **a)** the date of metastatic lung tumor progression (new lung tumors or local tumor failure of the index tumor), **b)** the date of death with local control of the index tumor, or **c)** the date of last follow up in patients who were still alive with local tumor control of the index tumor. Patients who are alive will be censored at the date of their last visit. Patients who have died from causes other than local failure of the index tumor will be censored at the time of death. Lung disease-specific survival rates will be summarized by using Kaplan-Meier methodology.
- **Overall survival rate** is defined as the time in days from the first cryoablation procedure to death. Patients who are alive will be censored at the date of the last visit. Overall survival rates will be summarized by using Kaplan-Meier methodology.
- **Time to metastatic lung disease progression beyond the index tumor** is defined as the time in days from the first cryoablation procedure to metastatic disease beyond the index tumor site. Patients without metastatic lung disease progression will be censored at the date of their last visit or their date of death (due to any cause). Metastatic progression free survival rates will be summarized by using Kaplan-Meier methodology.

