Efficacy of cryoablation on local tumor control for each index tumor in patients with pulmonary metastatic disease undergoing additional cryoablation treatment(s) of a previously treated index tumor will be summarized using the proportion of tumor control at 12-months post re-treatment and a 95% CI.

Technically successful treatment

A technically successful treatment will be defined by an ablation volume, ground glass opacity, or frank consolidation encompassing the targeted index tumor(s) within 30 days of the cryoablation procedure. Technical success will be calculated on a per-tumor level as well as a patient level. To be considered a technical success on a patient level all tumors treated during the baseline procedure must meet the technical success criteria. Technical success rates and 95% CIs will be calculated using random effects logistic regression on a tumor level and logistic regression on a patient level.

Disease recurrence or progression

The reference date for disease progression evaluation will be associated with the initial (first) cryoablation procedure done per study protocol. In the event of multiple cryoablation procedure dates, such as with bilateral lesions or staged treatments, the date of reference for disease progression evaluation will be the initial (first of n) cryoablation procedure.

- **Local disease progression** will be determined locally by evidence of local tumor failure. Time to lung disease progression will be summarized by using Kaplan-Meier methodology.
- **Lung-disease-specific survival** rate is defined as the time in days from the first cryoablation procedure to death and **a)** the date of lung tumor progression (new lung tumors or incomplete response), **b)** the date of death without lung tumor progression, or **c)** the date of last follow up in patients who were still alive without lung tumor progression. Patients who are alive will be censored at the date of their last visit. Patients who have died from causes other than lung cancer will be censored at the time of death. Lung disease-specific survival rates will be summarized by using Kaplan-Meier methodology.
- **Overall survival** rate is defined as the time in days from the first cryoablation procedure to death. Patients who are alive will be censored at the date of the last visit. Overall survival rates will be summarized by using Kaplan-Meier methodology.

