- **Time to metastatic lung disease progression beyond the index tumor** is defined as the time in days from the first cryoablation procedure to metastatic disease beyond the index tumor site. Patients without metastatic lung disease progression will be censored at the date of their last visit or their date of death (due to any cause). Metastatic progression free survival rates will be summarized by using Kaplan-Meier methodology.
- **Time to overall cancer progression** is defined as the time in days from the first cryoablation procedure to cancer progression (i.e., any location of active cancer disease). Patients without cancer progression will be censored at the date of their last visit or their date of death (due to any cause). Overall cancer progression free survival rates will be summarized by using Kaplan-Meier methodology.
- **Time to untreatable metastatic lung disease control with cryoablation** is defined as the time in days from the first cryoablation procedure to the time when the metastatic lung disease cannot be treated with cryoablation. Overall time to untreatable metastatic lung disease progression rates will be summarized by using Kaplan-Meier methodology.
- **Time to untreatable metastatic lung disease control with focal therapy** is defined as the time in days from the first cryoablation procedure to the time when the metastatic lung disease cannot be treated by focal (e.g., ablation, surgery, SBRT) intervention for control of metastatic lung disease. Overall time to untreatable metastatic lung disease progression rates will be summarized by using Kaplan-Meier methodology.

Intra-procedural data

Initial cryoablation procedure information including the type of procedure, tumor size and number, cryoablation needle type and the number of each type of needle used, freeze and thaw times, procedure times, and anesthesia type will be summarized using descriptive statistics.

Physical performance and quality of life

Physical performance (KPS) and quality of life (SF-12) assessments will be made by examining the change in the baseline scores to those reported post-operatively and at follow-up visits. The KPS scale and each of the eight SF-12 domains will be summarized at each time point by descriptive statistics. Percent change from baseline for each measure will also be summarized by descriptive statistics.

Additional Data Summaries

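### Restarted visits after repeat cryoablation leave only re-treated patients at risk by about month 27, so later estimates of overall survival and of progression beyond the index tumor are unreliable

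*Protocol*

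**What the plan says.** **Visits.** Protocol 7 sets the standard schedule: "Each patient will undergo a total of 9 visits, including an initial/screening visit, the procedure visit, and 7 post-operative visits". The last of these is month 24. For a re-treated index lesion, Protocol 7.8 provides that "follow-up visits will restart per the study protocol and continue through the 24 month visit after the date of the repeat cryoablation treatment". The SAP repeats this under Tumor control (additional cryoablation).

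**Clock.** In Protocol 10.5.5, overall survival "is defined as the time in days from the first cryoablation procedure to death". For progression, "the date of reference for disease progression evaluation will be the initial (first of n) cryoablation procedure". A repeat procedure moves neither starting point.

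**Censoring.** The SAP states for overall survival: "Patients who are alive will be censored at the date of the last visit. Overall survival rates will be summarized by using Kaplan-Meier methodology". Protocol 10.5.5 has the same rule. Patients without metastatic lung progression beyond the index tumor are censored at their last visit or at death.

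**What is absent.** Neither document cuts the curves at a common time, names landmark times for them, or provides survival follow-up after the last scheduled visit.

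**The concern.** Kaplan-Meier estimation assumes that the patients still under observation at a given time represent those already censored. Here the visit rule decides who stays under observation. Patients without re-treatment leave at about month 24, and re-treated patients stay until 24 months after the repeat. A repeat at month 6, 12 or 18 keeps a patient in view to about month 30, 36 or 42 on a clock that started at the first procedure.

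Re-treated patients are a selected group. They will usually have had a local recurrence, and they also lived long enough and were fit enough for another procedure. The first feature suggests a worse outlook and the second a better one. Once only these patients remain, the curve applies their hazard to the whole cohort. At stake are survival and progression rates quoted beyond month 24, and any median read from that part of the curve.

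**Working it through.** **1. The plan's own figures.** The documents give no figure for the Kaplan-Meier analyses. The stated design (203 tumors, reject at 181 or more, 84% against 91%) reproduces: one-sided alpha 0.0239, power 0.8501, and 203/0.90 = 225.6, rounded up to 226. It concerns the 12-month primary endpoint and is not an input here.

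**2. Latest visit without re-treatment.** The window is "Months 3, 6, 12, 18 and 24 visit window +/- 30 days". Visits count from the most recent procedure, and staged initial treatment may take up to 8 weeks (Protocol 7, Table 1 notes).

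- Not staged: 24 + 30/30.44 = 25.0 months from the first procedure.
- Staged: 24 + 56/30.44 + 30/30.44 = 26.8 months.

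Beyond about month 27, under the schedule, everyone still at risk has been re-treated.

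**3. Where the median would fall.** Protocol 3.2 cites 91% survival at 1 year and 59.6% at 3 years in a colorectal-metastasis series.

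- Year-1 hazard: −ln(0.91) = 0.0943.
- Hazard in years 1–3: ln(0.91/0.596)/2 = 0.2116 per year.
- S(24 months) = 0.91 × exp(−0.2116) = 0.736.
- Median = 2 + ln(0.736/0.5)/0.2116 = 3.83 years, about 46 months.

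**4. Size of the risk set.** The documents give no re-treatment rate for this trial. At the design's 9% failure rate, 0.09 × 203 is about 18 tumors. If all are re-treated, in different patients, that is 18/150 = 12% of patients; if half are, 6%. Further assumptions: repeat at month 6, 12 or 18, 25% of patients staged, visits spread over ±30 days, no dropout. Simulating 150 patients with the hazards in step 3:

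| Month from first procedure | At risk |
|---|---|
| 24 | about 70 |
| 25 | 18–25 |
| 27 | 5–14, all re-treated |

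A second simulation used exponential survival with a 48-month median, 10% re-treated at a time uniform over months 3–18, and 10% withdrawal per year. It gave 54 at risk at month 24 (16% re-treated), 17 at month 25 (49%), 10 at month 26 (82%), 8 at month 27 (100%) and 3 at month 36.

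**5. Effect on the estimates.** In the second simulation, the month-24 estimate matched the truth to within 0.001 in every scenario. At month 36:

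| Hazard ratio after re-treatment (assumed) | Kaplan-Meier | True | Difference |
|---|---|---|---|
| 0.5 | 0.651 | 0.607 | +4.4 points |
| 1 | 0.595 | 0.594 | +0.1 |
| 2 | 0.500 | 0.576 | −7.6 |

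On the cited survival with 6–12% re-treated, the month-35 estimate is about 8–9 points low at a hazard ratio of 2 and about 5 points high at 0.5. At 1 it is unbiased, with a standard deviation of about 9–13 points. For comparison, the standard deviation at month 24 in the second simulation is 4 points.

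**6. Medians.** A true median of 18 months is recovered without bias in every scenario (for example 17.4 against 17.4). A true median of 45.2 months (hazard ratio 2, 10% re-treated) is estimated at 36.0.

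**The case against.** The strongest reply is that nothing inside the planned 24 months is wrong. These are descriptive outcomes without a hypothesis test. No median or 36-month rate is named as an output, and the latest efficacy time the plan names is month 24. Bias also requires a hazard that differs after re-treatment, and the documents give no such figure. Their background points if anything the favorable way: a small series reports five repeat treatments without local recurrence, and an endobronchial series reports mean survival of 15 months with two sessions against 8.3 with one. Both settings differ from this one and neither settles the matter.

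Most of this stands and limits the point. It does not remove it. A Kaplan-Meier summary with no end time runs to the last observation and yields a median wherever the curve crosses 50%. Numbers at risk and confidence limits show that the tail is thin, but not that it is selected. Nor does it help that the restart is written per lesion: survival is a patient-level outcome, so a restarted visit is also that patient's last visit.

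A reader might also infer double counting of Karnofsky scores. Re-treated patients acquire a second set of visits, and the SAP says "The KPS scale and each of the eight SF-12 domains will be summarized at each time point by descriptive statistics". No text says that the restarted records would be pooled with the first set, and SF-12 is expressly not collected around a repeat. That inference is not supported.

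**Conclusion.** The point holds for overall survival and for time to metastatic lung progression beyond the index tumor. From about month 25 the risk set shrinks quickly, and by about month 27 it contains only re-treated patients, about 5–14 of 150 under the 6–12% assumption. Later rates, and any median read there, are very imprecise. They are also biased, in an unknown direction, if re-treated patients' hazard differs. The sizes rest on assumed re-treatment rates and timing, assumed hazard ratios, and survival like that cited in the protocol.

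Four stronger readings are tempting, and the documents do not support them:

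- *Every median is biased.* One reached before month 24 is unaffected.
- *Only re-treated patients remain straight after month 24.* Staging and visit windows delay this to about month 27.
- *The curves are shown to be biased.* With equal hazards they are only imprecise.
- *All the time-to-event curves share the problem.* Where local failure is itself the event (local progression, lung-disease-specific survival as the protocol defines it, and probably overall cancer progression), patients re-treated for failure have already left the risk set. The two untreatable-disease times have no stated censoring rule, so the effect on them cannot be determined.

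The 12-month primary endpoint and its sample size are not affected.

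**What to change.** Add to the SAP, under Disease recurrence or progression:

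*Patient-level Kaplan-Meier outcomes timed from the first procedure are administratively censored at 24 months from that procedure, whether or not an index tumor was re-treated. A median not reached by then is reported as not reached.*

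Use the restarted visits only for the SAP's separate analysis of tumor control after additional cryoablation.

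The cost is one sentence. It needs no new data and changes no visit or treatment rule. Estimates up to month 24 stay as they are. The small downside is that follow-up after month 24 is listed but not used in the curves.
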